**Project Title: Exploration of responses to compassion in a clinical population**

**NCT number: TBC**

**Date: 20th March 2018**

### **Project executive summary**

This project focuses on exploring responses to compassionate imagery, a technique from Compassion Focused Therapy (CFT; Gilbert, 2014). Evidence has documented that CFT decreases depression, shame, self-criticism and increases self-esteem (Kirby, 2016). Compassion-focused imagery (CFI) is a key technique in CFT, which involves visualizing compassion towards others, or imagining people, places or objects directing compassion towards oneself. Single trials of CFI have shown a reduction of negative affect and physiological changes associated with the attenuation of threat-focused behaviors (e.g. Rockliff et al., 2008). Regular CFI practice has increased self-compassion and reduced negative affect in both clinical and non-clinical populations (Gilbert & Irons, 2004; McEwan & Gilbert, 2016). Unfortunately, CFI can create threat-focused responses in some individuals. However, these findings have been based on tasks involving receiving compassion from others.

The present study therefore aimed to explore participants' responses to imagery exercises involving self-compassion, in comparison to a relaxation task (to control for certain task demands but without the compassion element), and a control task ( reading a magazine).

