### **SPECIFIC OBJECTIVES**

1. How do clinical participants initially respond to *self*-compassionate imagery in an initial trial, compared to relaxation and a control task? (using self-report and HRV measures)
2. Do any threat responses reduce following repeated trials of self-compassionate imagery?

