#### **Data analysis**

Paired *t*-tests will be run (i) to estimate differences in HRV during the self-compassion imagery, relaxation imagery and the control task, (ii) to examine changes in self-reported positive and negative affect from pre-CFI to post-CFI, (iii) to explore whether changes in positive and negative affect during CFI are greater or smaller from Trial 1 to Trial 3.

To complement group-level analyses, we will use reliable and clinically-significant change analyses. We will firstly report how many participants show a reliable change (Jacobson & Truax, 1991) in positive or negative affect following CFI.

We will also calculate how many individuals show a clinically-significant HRV response ( $\geq 5$ ms change in RMSSD within one individual between two different tasks).

Finally, we will report the number of positive and negative clinically-significant responses for both relaxation and compassion in each trial, in order to (i) compare effects of compassion versus relaxation at trial 1, and (ii) explore whether repeated trials improved response to each task.

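### Every planned threat measure is a within-session difference, so a reference level that shifts between sessions goes unseen and can be misread as a changed threat response

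*Combined protocol and SAP*

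**What the plan says.** Under Specific objectives, the second question is "Do any threat responses reduce following repeated trials of self-compassionate imagery". The Data analysis section offers these analyses that could bear on it:

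- paired *t*-tests "to estimate differences in HRV during the self-compassion imagery, relaxation imagery and the control task", with the trial not stated;
- paired *t*-tests "to examine changes in self-reported positive and negative affect from pre-CFI to post-CFI";
- a paired comparison across trials, "to explore whether changes in positive and negative affect during CFI are greater or smaller from Trial 1 to Trial 3";
- a report of "how many participants show a reliable change (Jacobson & Truax, 1991) in positive or negative affect following CFI";
- a count, per trial and for relaxation and compassion separately, of positive and negative HRV responses, where a response is a 5 ms or larger "change in RMSSD within one individual between two different tasks".

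The Procedure section fixes the order in every session as control task, relaxation, CFI, with HRV recorded in all three. The depression, anxiety and self-criticism scales (ODSIS, OASIS, FSCRS) are placed only at online screening. Randomization (Design section) is to three or four trials, and every session includes CFI.

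The plan does not name the reference task for the 5 ms rule, and it does not say when in the session pre-CFI affect is rated.

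**The concern.** Each listed quantity is a CFI (or relaxation) value minus a reference value from the same session. None compares the control-task RMSSD, the CFI RMSSD, or the pre-CFI or post-CFI affect of Trial 3 with that of Trial 1. A smaller difference at Trial 3 can therefore mean that CFI has become less threatening, or that the participant was already more threatened when the reference was taken.

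The fixed order makes such a shift plausible. From the second session on, a participant who found CFI unpleasant can anticipate it while the control and relaxation tasks are being recorded. Habituation would act the other way: first-session nervousness depresses the Trial 1 reference, and when it wears off an unchanged CFI value looks like new threat.

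The stake is the answer to Objective 2. The per-trial counts are meant to show whether repeated trials improve the response, and the Measures section already expects relaxed or neutral responses from everyone after three or four trials. An artefact in that direction could pass as confirmation. No CFI-free group shows how reference levels drift by themselves, and no symptom scale is stated to be repeated.

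**Working it through.** **The plan's own figures.** The sample of 25 rests on similar studies. No alpha, power, effect size or SD is given, so there is no calculation to reproduce. The inputs taken from the plan are N = 25 and the 5 ms threshold. Every RMSSD mean and SD, every affect score and every shift below is an assumption.

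**Identity.** Let the response at trial *t* be D_t = CFI_t − Ref_t. Then

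D_3 − D_1 = (CFI_3 − CFI_1) − (Ref_3 − Ref_1).

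The plan looks only at the left side. Suppose reference RMSSD falls by *s* between Trials 1 and 3, and a share *k* of that fall also appears during CFI. Then D_3 − D_1 = −ks + s = (1 − k)s.

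**One participant, RMSSD in ms.** Trial 1: control 40, CFI 32, D = −8, a negative response.

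| Trial 3 scenario | Control | CFI | D | Reading under the plan |
|---|---|---|---|---|
| s = 6, k = 0.25 | 34 | 30.5 | −3.5 | negative response gone, though both levels are worse |
| s = 6, k = 1 | 34 | 26 | −8 | no change, though both levels are worse |
| s = 6, k = 1.25 | 34 | 24.5 | −9.5 | more threat |
| reference up 4, CFI unchanged | 44 | 32 | −12 | more threat, though CFI is unchanged |

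**Affect.** Threat raises the pre-CFI negative-affect score, so the sign of the reference shift is reversed, but the logic is the same. Suppose negative affect goes from 15 to 22 at Trial 1 (+7) and from 21 to 23 at Trial 3 (+2). The Trial 1 to Trial 3 test sees a response 7 − 2 = 5 points smaller. The level before CFI is 21 − 15 = 6 points higher, and after CFI 23 − 22 = 1 point higher.

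**Group counts.** Take D as normal with mean −4 ms at Trial 1. The expected number of negative responders is 25 × Φ((−5 − mean)/SD).

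- SD 6, Trial 1: 25 × Φ(−1/6) = 10.8.
- s = 6, k = 0.5: the mean of D moves to −4 + 3 = −1, giving 25 × Φ(−4/6) = 6.3, while CFI RMSSD is 0.5 × 6 = 3 ms lower.
- Reference up 4, CFI unchanged: the mean of D moves to −8, giving 25 × Φ(3/6) = 17.3.
- k = 1, any s: the count stays at 10.8.

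| SD of D (ms) | Trial 1 | Reference falls 6, half carried | Reference rises 4, CFI unchanged |
|---|---|---|---|
| 4 | 10.0 | 4.0 | 19.3 |
| 6 | 10.8 | 6.3 | 17.3 |
| 8 | 11.3 | 7.7 | 16.2 |

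**The case against.** The best defence is that a within-session difference is the right measure of a response. Both objectives ask how people respond to the imagery, and the relaxation and control tasks are there to provide a same-day comparison. Absolute levels carry day-to-day stress and familiarity with the laboratory, so they are noisier across sessions. The study is exploratory, the affect comparison is worded neutrally, and only the responder counts speak of improvement. All of this stands, and it is why the change scores should remain the measure of response.

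The illustrations also depend on chosen values. The individual CFI worsening in the first scenario is 1.5 ms, below the plan's own 5 ms threshold, and the control task is assumed as reference. That limits any claim about size. It does not remove the ambiguity, which follows from the identity and is the same if relaxation is the reference.

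A reader might infer that threat building up between sessions will be scored as reduced threat. The documents do not support that. It requires the reference to worsen more than the CFI value. Equal worsening reads as no change, a larger worsening during CFI reads as more threat, and habituation pushes the other way, so the net direction is unknown. Nor do the documents show that any build-up occurs. The Project executive summary does say that "CFI can create threat-focused responses in some individuals", but its next sentence ties that evidence to receiving compassion from other people, whereas this study uses self-compassion.

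**Conclusion.** The concern holds as a gap in the analysis, without a predicted direction. All planned threat measures are within-session differences, so the plan cannot tell a changed CFI level from a changed reference level. Under the assumed values the expected negative-responder count among 25 could fall by 3.6 to 6.0 (SD 8 to SD 4) while CFI RMSSD worsens by 3 ms, or rise by 4.9 to 9.3 (the same SD range) with CFI RMSSD unchanged. With full carry-over the counts do not move, although threat is higher throughout. These figures rest on a normal distribution of D, a Trial 1 mean of −4 ms and the stated shifts, none of which comes from the documents.

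This is no reason to distrust the change scores as measures of acute reactivity. It is a reason not to conclude from them alone that repeated CFI has become less, or more, threatening.

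**What to change.** In the Data analysis section, keep the planned change-score tests and responder counts, and add beside them:

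1. Paired Trial 3 minus Trial 1 differences, reported descriptively with confidence intervals, in pre-CFI and post-CFI positive and negative affect, and in RMSSD for each task (control, relaxation, CFI).
2. A commitment to state, when interpreting Objective 2, whether a changed response reflects a changed CFI level, a changed reference level, or both.
3. A flag for each participant whose change score and level disagree, for example a smaller pre-to-post rise in negative affect with a higher post-CFI score.

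Do not turn the levels into a pass/fail condition, such as accepting a reduced response only if post-CFI negative affect is no higher and CFI RMSSD no lower than at Trial 1. Judged on point estimates with no true change in level, each would be worse by chance about half the time. The condition would then block the conclusion in about 50% of cases if the two measures were fully dependent, and 1 − 0.5 × 0.5 = 75% if they were independent. It would also reject a fall in response from +7 (15 to 22) to +1 (23 to 24) that occurred on a stressful day.

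No new measurement is needed. HRV is recorded in every task of every session, the affect comparison already requires pre- and post-CFI ratings at Trials 1 and 3, and everyone is assigned at least three trials. The cost is a few more descriptive estimates, and these will be imprecise: at an assumed two-sided 5% level, 25 pairs give 80% power only for a shift of about 0.58 SD of the paired differences, and levels vary more between days than within-session changes do.

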### Measures:

See Appendix 2 for copies of the questionnaires that we intend to use that are not validated.

- 1. Demographics**
- 2. Self-report form – Physiological variation**
- 3. Overall Depression Severity and Impairment Scale (ODSIS)**
- 4. Overall Anxiety Severity and Impairment Scale (OASIS)**
- 5. Forms of Self-Criticism/Attacking and Self-Reassuring Scale (FSCRS)**
- 6. Positive and negative affect generated**

**7. Heart Rate Variability (HRV).** Heart rate variability (HRV) is a physiological measure that allows us to quantify small changes in anxiety moment by moment, that a questionnaire cannot quantify. In this study it will allow us to measure whether participants respond to compassion with a threat-based response or a relaxed response (we expect that after 3-4 trials, all participants will respond with relaxation or a neutral response, but we predict that at the start, some will respond with threat-based responses).

We will use the BioPac system to collect HRV data. Electrodes will be placed using the Lund guidance which is considered the most stable, least invasive, and with high diagnostic accuracy. Using the program Acqknowledge, we will analyse beats per minute (BPM) and ratios of sympathetic and parasympathetic activity. Specifically, we will use the Root Mean Square of the Successive Differences (RMSSD) of RR intervals (Task Force of the European Society of Cardiology and the North American Society of Pacing and Electrophysiology, 1996). RMSSD was selected because there is no agreed clinically-significant change value for analysing HF HRV data (see Data analysis section).

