#### Procedure

Participants will complete an initial screening questionnaire online including: an informed consent (see Appendix 1), demographics questions, ODSIS, OASIS and FSCRS. Eligible participants will be invited to attend in-person sessions. In each session, HRV will be measured by a research assistant whilst the participant engages in three 4-minute tasks in the following order:

- **Control task:** participants will read a magazine with neutral content for 4 minutes
- **Relaxation imagery** (see appendix 3): participants will complete a relaxation exercise of beach or forest imagery for 4 minutes.
- **Compassion-focused imagery:** participants will complete a compassion-focused imagery for 4 minutes (see appendix 3).

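### Individual HRV responses are counted at a fixed 5 ms RMSSD difference with no allowance for measurement error and no chance benchmark, although affect gets a reliable-change criterion (minor, cheap to improve)

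*Combined protocol and SAP*

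**What the plan says.** The Data analysis section sets out two kinds of individual-level analysis: "To complement group-level analyses, we will use reliable and clinically-significant change analyses". For affect it will report "how many participants show a reliable change", using the Jacobson-Truax method. For HRV it will calculate "how many individuals show a clinically-significant HRV response": a person counts as a responder if there is a 5 or more "ms change in RMSSD within one individual between two different tasks". The section then says "we will report the number of positive and negative clinically-significant responses for both relaxation and compassion in each trial", to compare compassion with relaxation at Trial 1 and to look at change over repeated trials.

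The Measures section explains the choice of index: "RMSSD was selected because there is no agreed clinically-significant change value for analysing HF HRV data". This implies that the authors take 5 ms as an agreed value for RMSSD. It does not say whether that value allows for measurement error. Under Procedure, in each session "the participant engages in three 4-minute tasks in the following order", so each task gives one short recording per session.

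Specific objective 2 asks: "Do any threat responses reduce following repeated trials of self-compassionate imagery". The Measures section expects some threat-type responses at the start and only relaxed or neutral ones after 3-4 trials.

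**The concern.** Whether a change is large enough to matter and whether it exceeds measurement error are separate questions. The plan asks both for affect but only the first for HRV. No RMSSD reliability, error SD, expected chance count, interval or test accompanies the HRV counts.

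These counts are also the only HRV analysis explicitly tied to change across trials. The paired t-tests of HRV compare tasks and name no trial, and the Trial 1 to Trial 3 t-test concerns affect. So on the HRV side, what can be said about individual threat or relaxation responders, and about a fall in threat responses, rests on counts with an unknown noise content. If noise is moderate, the predicted finding that some people respond with threat at the start would usually appear even with no true response.

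**Working it through.** The plan gives no derivation of 5 ms and no error SD, so there is no figure of its own to reproduce.

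**Inputs from the documents:** 25 participants (Participants and process of recruitment); 5 ms cut-off (Data analysis); one 4-minute recording per task per session (Procedure).

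**Assumed:** with no true task effect, a person's between-task difference is normal with mean 0 and standard deviation SD, independent between people. SD is not in the documents, so 2, 3, 5 and 8 ms are shown. The arithmetic is the same whichever two tasks are compared.

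**Break-even.** Two-sided false labelling is 2 × P(Z > 5/SD). It equals 5% when 5/SD = 1.96, so SD = 5/1.96 = 2.55 ms. For a single recording this is 2.55/√2 = 1.80 ms.

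**Chance responses in one direction, in 25 people.** Expected number = 25 × P(Z > 5/SD); percentile and probability from the binomial distribution.

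| SD (ms) | P(Z > 5/SD) | Two-sided rate | Expected negative responses | 95th percentile | P(at least one) |
|---|---|---|---|---|---|
| 2 | 0.006 | 1% | 0.2 | 1 | 14% |
| 3 | 0.048 | 10% | 1.2 | 3 | 71% |
| 5 | 0.159 | 32% | 4.0 | 7 | 99% |
| 8 | 0.266 | 53% | 6.6 | 10 | over 99% |

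Four negative responses in 25 would therefore be unusual at SD 3 (about a 3% chance of four or more) and the expected number at SD 5 (about 58%).

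**Effect on change over trials.** Suppose 5 of 25 truly drop 10 ms at Trial 1, the rest do not change, and nobody truly changes at Trial 3 (assumed). The expected Trial 1 count is 5 × P(Z < 5/SD) + 20 × P(Z > 5/SD) = 5.1, 5.7, 7.4 and 9.0. At Trial 3 it is 25 × P(Z > 5/SD) = 0.2, 1.2, 4.0 and 6.6. The true fall of 5 shows as 4.9, 4.5, 3.4 and 2.3.

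**Noise can also lower a count.** Suppose 20 of 25 truly rise 7 ms and 5 do not change (assumed). The expected positive count is 20 × P(Z < 2/SD) + 5 × P(Z > 5/SD) = 16.9, 15.2, 13.9 and 13.3, against a true 20.

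**Can positive and negative counts check each other?** Pure noise would give similar numbers each way. A shift in the mean breaks this: with a uniform rise of 3 ms and an error SD of 5 ms per recording (difference SD 5 × √2 = 7.07), 25 × P(Z > 2/7.07) = 9.7 positive and 25 × P(Z > 8/7.07) = 3.2 negative responses are expected. All 3.2 negative ones are noise.

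**The case against.** The strongest reply has four parts.

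- *The harm is not shown.* The documents give no RMSSD level, SD or reliability. If the difference SD is 2.55 ms or less there is no material problem, and 5 ms may already allow for error. This stands: what is shown is an omission, not a bias. A reader might infer that 5 ms is too low; the documents do not support that.
- *The plan has a built-in check.* Positive and negative counts are reported for both imagery tasks in every trial, and noise of equal size creates no spurious difference between tasks or trials. This stands in part, so it would go too far to infer that the plan offers no way at all to gauge noise. But the check is informal, is not planned as one, and fails under a mean shift.
- *Noise does not simply inflate counts.* This stands. It adds false responses among people whose true change is below 5 ms, and loses some whose true change is above it. A reader might infer that all the counts will be too high; the second example above shows otherwise. Attenuation of true differences between trials remains.
- *The study is exploratory.* It is small, and the counts complement group-level tests. This stands and limits the severity. It does not remove the need to know how many responses called clinically significant could be noise.

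**Conclusion.** The point holds as a minor one with an inexpensive remedy. HRV responses are counted without an error criterion or chance benchmark, although the same section applies a reliability criterion to affect. The size of the problem cannot be known from the documents: across assumed difference SDs of 2 to 8 ms, chance alone gives 0.2 to 6.6 negative responders in 25, and a true fall of 5 responders would show as 4.9 to 2.3. These figures rest on normal, independent errors of equal size for everyone. What is affected is the statement that particular numbers of people showed threat or relaxation responses, and that these changed over trials. The group-level HRV tests and the affect analyses are untouched.

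**What to change.** Keep the 5 ms count and describe it as a size-of-change count. Then add the following to the Data analysis section.

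1. Estimate s, the pooled within-person SD of control-task ln RMSSD across Trials 1-3. With full attendance this has 25 × (3 − 1) = 50 degrees of freedom.
2. Beside each count, by task, trial and direction, report the number expected by chance: the sum of P(Z > 5 / (√2 × s × the participant's mean control-task RMSSD)) over the participants with both recordings in that trial. Give its 95th percentile.
3. State that this is a conservative (upper) benchmark because s includes day-to-day variation, provided imagery recordings are no noisier than control recordings.
4. Say that a count exceeds noise only if it is above that 95th percentile. Otherwise report it descriptively, and do not read it as evidence of individual threat or relaxation responders. A count below the percentile is not evidence that there were none.

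A noise estimate from blocks within each recording, and a count of changes that are both 5 ms or more and reliable, are optional sensitivity results.

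**Cost.** A few lines of text and a small analysis of recordings already planned. Three trials, two tasks and two directions give 3 × 2 × 2 = 12 benchmarks, plus four for the subgroup with a fourth trial. The benchmark may be large or too strict. At an assumed RMSSD of 40 ms, s = 0.05, 0.10, 0.15 and 0.25 give difference SDs (√2 × s × 40) of 2.8, 5.7, 8.5 and 14.1 ms. The expected chance responses are then about 1.0, 4.7, 6.9 and 9.0 of 25 per direction, with 95th percentiles of 3, 8, 11 and 13. Statements about individuals become more cautious. The benchmark judges the count and does not identify which people are true responders. Drift from the fixed task order is not removed.

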### **METHODS**

### Participants and process of recruitment:

We plan to recruit a sample of 25 participants for this study, based upon other studies of compassionate imagery with similar designs (Rockliff et al., 2008; Duarte et al., 2015).

Inclusion criteria are:

1. Clinical level of anxiety or depression (defined for this study  $\geq 8$  on the OASIS or ODSIS)
2. High self-criticism (we selected a cut-off of 0.5 standard deviations above the mean in self-inadequacy or self-hatred on the FSCRS). Based upon a validation in Colombia of the FSCRS by Naismith, Duran Ferro, Ingram, & Jiménez Leal (Submitted), this represents  $\geq 24$  in self-inadequacy or  $\geq 8$  in self-hatred.

These criteria were selected because these interventions are designed to help a clinical population presenting with high self-criticism. Offering this to a non-clinical population (i) reduces the likelihood of observing significant changes, and (ii) will not allow us to help those who present with higher needs.

Nonetheless, those who complete the initial screening and do not meet inclusion criteria will be invited to a group session to learn compassion techniques. They will also receive compassion materials via email at the end of the study.

For recruitment, posters will be hung inside the campus of the University of the Andes. The same information will be published in university social media pages.

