### Design:

Participants will be randomized to complete 3 or 4 trials (see details below) using a 2:1 ratio, using a randomization sequence drawn up prior to the study start. This will allow us to explore in a small subgroup whether a fourth trial impacts results. We are also running a related study, which will explore the effects of psychotherapy that will be offered following these 3-4 trials, and we anticipate that a fourth trial will increase probability of dropout from the second study, therefore we will not assign all participants to do the fourth trial.

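### Objective 2 is judged from raw per-trial counts with no denominator or common set of participants, so lost participants and the smaller Trial 4 group lower the threat count even if nobody's response changes

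*Combined protocol and SAP*

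**What the plan says.** The second specific objective asks: "Do any threat responses reduce following repeated trials of self-compassionate imagery". The Measures section, under heart rate variability (HRV), sets out the expected course: "we predict that at the start, some will respond with threat-based responses", and later "we expect that after 3-4 trials, all participants will respond with relaxation or a neutral response".

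The Data analysis section has two analyses that run across trials:

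- Paired t-tests of whether the change in positive and negative affect during compassion-focused imagery (CFI) differs between Trial 1 and Trial 3. These are on affect; no Trial 1 to Trial 3 test of HRV is listed.
- A tally: "we will report the number of positive and negative clinically-significant responses for both relaxation and compassion in each trial". One stated use of it is to see whether repeating the trials improved the response to each task. For HRV, a response is a change of at least 5 ms in RMSSD between two tasks.

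On numbers, the recruitment section says "We plan to recruit a sample of 25 participants for this study, based upon other studies of compassionate imagery with similar designs". The Design section says "Participants will be randomized to complete 3 or 4 trials (see details below) using a 2:1 ratio", and of the fourth trial, "This will allow us to explore in a small subgroup whether a fourth trial impacts results". No section gives a dropout rate, a missing-session rule or an analysis set for this study. The only mention of dropout is "we anticipate that a fourth trial will increase probability of dropout from the second study", which concerns the related psychotherapy study.

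**The concern.** The HRV answer to Objective 2 rests on comparing counts between trials. A count has two parts: how many people attended and what share of them responded negatively. The plan does not separate the two. If fewer people attend Trial 3 than Trial 1, the number of threat responses falls for that reason alone. If those who leave are more often those who had a threat response, the share among attenders falls as well, and adding a denominator does not fully repair it.

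The fall runs in the direction that the plan expects, towards no threat responses after 3-4 trials. With 25 participants, the loss of two or three threat responders could change the conclusion. The study could then report that repetition reduces threat when the change is only in who was counted.

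**Working it through.** The plan gives no figure to reproduce: the sample size rests on precedent, with no threat rate, dropout rate or between-trial correlation.

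**Inputs from the documents.** N = 25; allocation 2:1, so about 25/3 = 8 people have a Trial 4; raw numbers reported per trial.

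**Assumed inputs.** Threat rate 30% (20% to 40% also tried); chance of leaving after each trial as shown below. The null throughout is no true change over trials.

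**1. Loss unrelated to response, 20% after each trial.**
- Attenders: 25, then 25 × 0.8 = 20, then 20 × 0.8 = 16.
- Expected threat count at 30%: 7.5, 6.0, 4.8.
- The proportion stays at 30%. The count falls by (7.5 − 4.8)/7.5 = 36%, and a denominator would reveal this.

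**2. Leaving more common after a threat response, 50% against 5%.**

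If each person's response is the same at every trial (correlation 1.0), this can be done by hand:
- Threat responders: 7.5, then 7.5 × 0.5 = 3.75, then 3.75 × 0.5 = 1.875.
- Others: 17.5, then 17.5 × 0.95 = 16.63, then 16.63 × 0.95 = 15.79.
- Proportion at Trial 3: 1.875/(1.875 + 15.79) = 10.6%, against 30% at Trial 1.

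With imperfect correlation, simulation (normal responses, threat defined as the top 30%, equal correlation between all trials) gives:

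| Leaving after threat / otherwise | Correlation | Count, Trial 1 to Trial 3 | Proportion of attenders, Trial 1 to Trial 3 |
|---|---|---|---|
| 50% / 5% | 0.5 | 7.5 to 3.9 | 30% to 23% |
| 50% / 5% | 1.0 | 7.5 to 1.9 | 30% to 11% |
| 20% / 5% | 0.5 | 7.5 to 5.7 | 30% to 28% |
| 20% / 20% | any | 7.5 to 4.8 | flat at 30% |

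With zero correlation between trials, the proportion also stays at 30%.

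**3. Trial 4 with no dropout at all.** 25/3 × 0.30 = 2.5 expected threat responses, against 25 × 0.30 = 7.5 at Trial 1. This fall is built into the design.

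**4. The paired Trial 1 to Trial 3 comparison.** Each person is compared with themselves. Under the same null, the mean Trial 3 minus Trial 1 threat score in completers was +0.09 SD (50%/5%, correlation 0.5) and 0 at correlation 1.0. Over all the informative scenarios run it lay between 0 and about +0.23 SD, never towards a reduction. In the first of these cases the completers' threat proportion goes from about 16% to about 23%. The cause is regression to the mean: people with a high Trial 1 value have been removed.

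A paired test would overstate improvement only if leavers would have improved less. For example, suppose 70% improve by 0.5 SD, 30% do not improve, and half of the latter leave. The mean change is −0.7 × 0.5 = −0.35 SD in everyone and −0.35/(0.70 + 0.15) = −0.41 SD in completers.

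**5. Why following only the Trial 1 negatives is not the answer.** Take an assumed threat rate of 24% (6 of 25), normal responses, no true change and no dropout. The share of Trial 1 negatives that are not negative at Trial 3 is about 63%, 53% and 41% at correlations of 0.3, 0.5 and 0.7. If 40% of them leave and are counted as unresolved, the 53% becomes 0.6 × 53% = 32%. A resolved share alone therefore suggests benefit where there is none. With no dropout and no true change, newly negative responses balance the resolved ones.

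**The case against.** Several points on the other side stand.

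- **Selective leaving is not documented.** Nothing says that threat responders are likelier to leave. A change of 5 ms in RMSSD need not be felt as distress, and the psychotherapy offered after the trials could encourage attendance. The Design section's remark concerns a fourth trial and dropout from the second study, so it is not evidence of loss before Trial 3 here.
- **The work is exploratory.** The plan has no rule that scores a leaver as resolved, and the authors may well report attendance beside each count. If loss is unrelated to response, n/N is enough for Trials 1 to 3.
- **The sizes are assumed.** Under milder selective leaving (20% against 5%), the proportion barely moves. If everyone attends Trial 3, the Trial 1 to Trial 3 counts are sound.

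A reader might infer that attrition alone also produces a false reduction in the paired Trial 1 to Trial 3 tests. The documents do not support that. Those tests compare the same people, and on affect rather than HRV; under no true change the bias is zero or towards an increase.

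None of this answers the central point. The plan compares raw numbers between trials, names no common set of participants, and includes a Trial 4 to which about two thirds are never assigned.

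**Conclusion.** The point holds for the per-trial counts. Any loss of participants lowers them without any change in response, and the Trial 4 count falls to about one third of the Trial 1 count by design. The size of the dropout effect is unknown. It was 7.5 to 4.8 under 20% unrelated loss after each trial, and 7.5 to 3.9 under strongly selective loss at correlation 0.5; both rest on an assumed 30% threat rate. Bias in the proportions needs two further conditions: leaving linked to threat, and responses correlated between trials. That is a risk and not a documented fact.

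For the paired affect tests the limitation is one of representativeness. They cannot speak for those who left, and they would overstate improvement only on the added assumption that leavers would have improved less. The change is worth making before analysis, because the counts are the only listed HRV analysis across trials and their weakness favours the expected result.

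**What to change.** In the Data analysis section:

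1. Report n/N for each trial and task. Compare Trial 4 with earlier trials only within those assigned to four trials.
2. Base Objective 2 on a within-person Trial 1 by Trial 3 cross-tabulation for CFI, once by the RMSSD rule and separately by reliable worsening of affect. Show resolved, persistent, newly negative, and left before Trial 3. Judge reduction by comparing resolved with newly negative among participants with both trials (a paired, McNemar-type comparison), not by the resolved share of Trial 1 negatives. With 25 participants the discordant pairs will be few, so give the counts themselves.
3. Report the Trial 1 responses of those who left. As a sensitivity analysis, repeat the comparison with leavers keeping their Trial 1 response. This puts them in the unchanged cells: the resolved and newly negative counts stay as they were, but the net change is expressed over all 25.
4. State that the paired affect tests describe participants seen at both trials.

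The cost is one extra table from data already held. The stated reduction may become less favourable, partly because some people leave for unrelated reasons. Where leaving does follow a threat response, the completer comparison can lean towards an apparent increase, so it should be read beside the leavers' Trial 1 results.
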